### **1.3.Nutritional protocol and procedures**

Breast milk was the first option, according to our NICU enteral nutrition policy, and preterm infant formula was the second option if there was no or insufficient maternal breast milk. On the first day of life (DOL), minimal enteral nutrition was started at volumes of 10–20 ml/kg/day in infants under 1500 g and 21–40 ml/kg/day in infants over 1500 g. If achievable, the enteral nutrition volume was increased by 10–15 ml/kg/day until it reached 150–180 ml/kg/day. Orogastric feeding tubes were used to provide enteral nutrition. Very low birth weight (VLBW) infants and those for whom enteral feeding was insufficient to achieve an energy supply of 120–150 kcal/kg/day had total parenteral nutrition started on the first day of life in accordance with nursery protocol. All infants were fed in accordance with our institution's NICU nutritional protocol.

### **1.4.Umbilical Venous Catheter Placement, Use, and Removal**

In our NICU, UVC placement is a sterile bedside procedure carried out by pediatric residents, neonatology fellows, and neonatology specialists, using polyurethane, single-lumen catheters sized according to the infant's weight: 3.5 Fr for those under 1500 g and 5 Fr for those over 1500 g. Catheter placement is performed using the Modified Shukla-Ferrara Formula. The position of the catheters is confirmed with chest and/or abdominal radiographs before they are secured. Fluids and medications administered through the catheter are prepared under sterile conditions, and unfractionated heparin at a concentration of 0.5 IU/ml is added to intravenous

fluids and parenteral nutrition solutions. The recommended maximum duration of catheter use in our unit is 7-10 days for UVC.

During follow-up, any catheter malposition, and the postnatal day on which it occurred, if applicable, were recorded. Malposition was defined as follows: The optimal placement of the UVC is at the junction of the inferior vena cava and the right atrium. This area corresponds to the T9-10 level on an anteroposterior chest film (8). In preterm infants, even a difference of one vertebral level on a direct radiograph can be significant. Therefore, in addition to thoracic vertebral levels, the level of the right hemidiaphragm can also be used as a reference point for the catheter tip on direct radiographs. Catheters positioned further intracardially or at a lower level are considered malpositioned (9).

## 2.5. Data collection

**(a) Demographics and clinical data:** Maternal obstetric diseases (hypertension, diabetes, premature membrane rupture, chorioamnionitis), and prenatal steroid administration were all included in the prenatal data. The following natal data were recorded: gestational age (GA), gender, birth weight, presence of small for gestational age (SGA), mode of delivery, 5th minute Apgar score, and need for resuscitation at birth, cord blood gas parameters (pH, HCO3, BE, lactate) and initial hemoglobin value. Gestational age was determined by asking about the last menstrual period and performing an ultrasonographic examination. According to Fenton et al. (7), SGA is defined as a birth weight less than the 10th percentile. Nutritional measurements including the time to first feeding, initial feeding type (breast milk, formula or mixed), time to reach full enteral feeding (FEF:120 ml/kg/day), and the presence of delayed passage of the first meconium (> 48 h) were recorded.

Clinical gastrointestinal and/or radiological findings observed during hospitalization were noted as vomiting, gastric residue (residual gastric volume exceeding 50% of the previous

feeding volume), abdominal distension, prominent bowel loops, occult or overt blood in the stool, bowel dilation, pneumatosis intestinalis, portal venous gas, and the presence of pneumoperitoneum in the abdominal radiography. These findings were evaluated both between the groups and within the UVC (+) group, comparing the periods when the catheter was in place and after its removal.

Postnatal morbidities such as respiratory distress syndrome (RDS), hemodynamic significant patent ductus arteriosus (HsPDA), grade 2-3 intraventricular hemorrhage (IVH), FI, NEC, and sepsis were noted. Gastric residual volume of more than 50% of the previous feeding volume, emesis, abdominal distention, or both, and a reduction, delay, or cessation of enteral feedings were the criteria used to define feeding intolerance (8). According to the modified Bell's criteria (9), stage II/III NEC was used as an outcome parameter. Echocardiography was used to determine the presence of HsPDA. Positive blood culture was used to define proven sepsis. The Papile classification system was used to classify IVH (10). Furthermore, the need for inotropic support during the first week of life, parenteral nutrition durations, invasive/non-invasive mechanical ventilation support, total respiratory support, oxygen support, hospitalization, and mortality were recorded.

**(b) Splanchnic near-infrared spectroscopy (NIRS) monitoring:** As soon as the infants were admitted to the NICU on the first day of life (DOL), a self-adhesive transducer (cerebral/somatic-neonatal NIRSensor) with a light-emitting diode and two remote sensors was applied to the infra-umbilical abdominal region to continuously record regional splanchnic saturation (rSO2S). Continuous rSO2S monitoring was carried out for 1 week using NIRS (INVOS 5100; Covidien Somanetics, Troy, MI), simultaneously together with continuous preductal oxygen arterial saturation (SaO2) monitoring using a pulse oximetry device (Nellcor, Covidien-Medtronic, Minneapolis, MN) with a target band of 90–95% and alarm settings of 89 and 96% in the case of oxygen therapy. Based on the simultaneous measurements of rSO2S and

$\text{SaO}_2$ , the infants' fractional tissue oxygen extractions ( $\text{FOE} = \text{SaO}_2 - \text{rSO}_2\text{S} / \text{SaO}_2$ ), which represent the balance between oxygen delivery and oxygen consumption, were assessed. After removing artifacts that may indicate sensor misplacement,  $\text{SaO}_2$  and NIRS parameters ( $\text{rSO}_2\text{S}$ ,  $\text{FOE}$ ) were calculated as means on each day of the first week of life (WOL).

Infants with an UVC were included in the UVC (+) Study Group, while those without a catheter were included in the UVC (-) Control Group. Continuous measurements taken during the first WOL were compared both between the groups and within each group on a day-to-day basis. Splanchnic NIRS monitoring was terminated 24 hours after the removal of the UVC. In the UVC (+) Group, the day and time of catheter placement and removal were recorded. Splanchnic oxygenation measurements were compared at the following time intervals: one hour before UVC placement, one hour after UVC placement, 24 hours before UVC removal, and 24 hours after UVC removal. Additionally, the daily means in the UVC (+) Group during the period when the UVC was in place were compared with the daily means in the UVC (-) Group. Clinical parameters and splanchnic NIRS data were compared between the UVC (+) and UVC (-) Groups. The birth hemoglobin (Hb) value of the UVC (+) Group, as well as the Hb value on the day the UVC was removed, were recorded, and a repeated measures analysis was performed.

The primary outcomes included comparing continuously recorded  $\text{rSO}_2\text{S}$  and  $\text{FOE}$  values during the first WOL between the UVC (+) and UVC (-) groups, assessing  $\text{rSO}_2\text{S}$  and  $\text{FOE}$  measurements within the UVC (+) Group before and after UVC placement and removal, and determining the impact of UVC on splanchnic oxygenation. The secondary outcomes involve evaluating the relationship between UVC presence and the incidence of feeding intolerance and necrotizing enterocolitis.

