### **1.5.2. Statistical analysis**

The statistical data were analyzed using IBM SPSS 21.0 software (IBM Corp. Released 2012. IBM SPSS Statistics for Windows, Version 21.0. Armonk, NY: IBM Corp.). The normality of variable distribution was assessed by Shapiro-Wilk test. The data were presented as a mean±standard deviation (SD), median (Q1–Q3), frequency, and percentage. For comparing normally distributed groups with two groups, the independent samples t-test was used. For comparing non-normally distributed groups with two groups, the Mann-Whitney U test was used. For comparing values at different time points, the Wilcoxon test was used when there were two groups, and the Friedman test was used when there were three or more groups. For repeated measurements, the two-way repeated measures ANOVA (One Factor Repetition) test was used. To determine the direction and magnitude of the relationship (correlation) between variables, Pearson correlation coefficients were calculated for normally distributed variables, and Spearman correlation coefficients were calculated for non-normally distributed variables. For the analysis of cross-tabulations, Pearson Chi-Square, Yates' Chi-Square, and Pearson Exact Chi-Square tests were used. The McNemar-Bowker test was used for comparing categorical clinical findings at two different time points. Covariance analysis was used to assess the importance of the model that had been installed with the confounding factors. A p-value of <0.05 was considered the criterion for statistical significance.

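### Nine individual gut findings, each compared between groups and within UVC (+), are held to p<0.05 with no outcome tier, exploratory label or multiplicity rule

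*Combined protocol and SAP*

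**What the plan says.** Section 2.5(a), on clinical data, opens the list with "Clinical gastrointestinal and/or radiological findings observed during hospitalization were noted as vomiting, gastric residue" and continues with "abdominal distension, prominent bowel loops, occult or overt blood in the stool, bowel dilation, pneumatosis intestinalis, portal venous gas, and the presence of pneumoperitoneum" on abdominal radiography. That makes nine findings. Two comparisons follow for each: "These findings were evaluated both between the groups and within the UVC (+) group, comparing the periods when the catheter was in place and after" removal.

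The outcomes paragraph at the end of section 2.5(b) makes the splanchnic oxygenation measures primary and then states: "The secondary outcomes involve evaluating the relationship between UVC presence and the incidence of feeding intolerance and necrotizing enterocolitis". The nine findings are in neither tier.

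The FI definition in section 2.5(a) begins "Gastric residual volume of more than 50% of the previous feeding volume, emesis, abdominal distention, or both" and goes on to require a change in enteral feeding.

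Section 1.5.2 names Pearson, Yates and exact chi-square tests for cross-tabulations. For the paired comparison it says: "The McNemar-Bowker test was used for comparing categorical clinical findings at two different time points". It closes with "A p-value of <0.05 was considered the criterion for statistical significance". No section gives a multiplicity adjustment, a testing sequence or an exploratory label.

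**The concern.** The nine findings are more than recorded data. The plan says they are compared in two ways, names tests that fit both, and gives a significance criterion that makes no exception for them. They all bear on one question: whether a UVC affects the gut.

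The family also contains a composite and its own parts. Gastric residue, vomiting and distension enter the FI definition and are compared singly as well. If FI shows no difference, a p<0.05 for distension alone, or for the in-place versus after-removal contrast, could still be reported as evidence that a UVC disturbs feeding or the bowel, and nothing in the plan prevents it. A multiplicity rule for the rSO2S and FOE primaries would not reach these tests.

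**Working it through.** **Inputs from the documents.** Nine findings and two comparisons each (2.5(a)); FI and NEC as secondary outcomes (2.5(b)); threshold 0.05 (1.5.2); 21 infants per group (1.5.1). The 21 was sized for a standardized effect of 0.8 at 80% power. A one-sided t-test reproduces it (20.03, rounded up to 21); a two-sided test would need 26. Sidedness is not stated. I take 21 as given, since the gut tests were not part of that calculation.

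**Step 1, count.** 9 × 2 = 18 comparisons of findings; 18 + 2 = 20 gut tests, of which 9 + 2 = 11 are between groups.

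**Step 2, reference value.** For k independent tests, each at a full 5%, P(at least one) = 1 − 0.95^k.

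| k | Tests | P(at least one) |
|---|---|---|
| 2 | FI and NEC | 9.75% |
| 11 | all between-group | 43.1% |
| 18 | findings only | 60.3% |
| 20 | all | 64.2% |

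This overstates the risk here, because small-sample tests of rare events do not reach 5% and the findings are correlated.

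**Step 3, true size of one test at 21 per group.** These are exact binomial calculations. McNemar assumes equal rates and independence between an infant's two periods, so the discordance probability is 2p(1 − p). The exact/Yates column uses Yates where the smallest expected count is at least 5, and the exact test otherwise.

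| Event rate (assumed) | Pearson | Exact/Yates | McNemar uncorrected | McNemar exact |
|---|---|---|---|---|
| 2% | 0.0010 | 0.0001 | 0.0010 | 0.0000 |
| 5% | 0.0132 | 0.0022 | 0.0135 | 0.0003 |
| 30% | 0.0559 | 0.0227 | 0.0427 | 0.0209 |

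**Step 4, combine.** Use 1 − Π(1 − αᵢ). Illustrative assumed rates: six commoner findings and FI at 30%, three rare findings at 2%, NEC at 5%.

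- All 20, uncorrected: 1 − (0.9441)^7 × (0.9990)^3 × 0.9868 × (0.9573)^6 × (0.9990)^3 = 49.5%.
- All 20, exact/Yates: 1 − (0.9773)^7 × (0.9999)^3 × 0.9978 × (0.9791)^6 = 25.2%.
- The 11 between-group tests: 1 − (0.9441)^7 × (0.9990)^3 × 0.9868 = 34.2% uncorrected; 1 − (0.9773)^7 × (0.9999)^3 × 0.9978 = 15.1% exact/Yates.
- FI and NEC only: 1 − 0.9441 × 0.9868 = 6.8% uncorrected; 1 − 0.9773 × 0.9978 = 2.5% exact/Yates.

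**Step 5, allow for correlation.** Simulation with correlated findings (latent correlation 0 to 0.6; six commoner findings at 15–45%, three rare ones at 1–5%) gives 39–48% uncorrected and 16–25% exact/Yates. A second set of rates (FI and its parts 20–40%; bowel loops, blood in stool and bowel dilation 10–30%; NEC and the radiological signs 2–8%), with correlation 0 to 0.8, gives 38–52% and 14–26%. Across all settings tried, including correlation between an infant's two periods, the range is about 35–58% uncorrected and 11–28% exact. FI and NEC alone stay at 5–9% and 2–3%.

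**The case against.** Several objections have force, and they limit the point.

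- **A reader might infer that a false positive is likely.** That needs something close to 20 independent tests at a full 5% each. Most settings fall below even odds, all exact-test settings do, and above 50% is reached only in some settings with uncorrected tests. Section 1.5.2 lists Yates and exact tests beside Pearson without a rule for choosing, so the uncorrected range should not be read as the expected result.
- **A reader might infer that FI and NEC carry no more weight than the other 18 tests.** The documents do not support this: section 2.5(b) names them as secondary outcomes below the NIRS primaries. What is missing is a status for the nine findings.
- **The count of 20 is a reading.** The plan says the findings were evaluated, and McNemar-Bowker can also handle more than two categories. Nine separate paired tests is the natural reading but is not stated. The comparison of clinical parameters between groups in 2.5(b) could equally add tests.
- **Correlation between an infant's two periods lowers the exact within-group error.** A within-infant correlation of about 0.5 cuts that part from about 5–13% to 2–8%. The between-group tests alone (22–37% Pearson, 10–16% exact under the second set of rates) still exceed 5%.
- **The overlap is partial.** FI also requires a change in feeding, so vomiting or residue alone need not be FI. It is tempting to add that pneumatosis, portal venous gas and pneumoperitoneum duplicate NEC, but the documents cite the staging criteria without reproducing them, so I do not rely on that.
- **This is an observational cohort with NIRS primaries.** The consequence is therefore confined to the gut conclusions.

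**Conclusion.** The concern holds in limited form. Nine gut findings are compared in two ways at p<0.05 with no tier, exploratory label or multiplicity rule, and three of them are parts of FI, so a null FI result could be bypassed through a component. With no UVC effect and 21 per group, the chance of at least one nominally significant gut result is roughly 11–28% with exact tests and 35–58% with uncorrected tests. The lowest figure is still more than twice 5%. The size depends on assumed event rates and correlations, on the choice among the tests listed, and on reading the comparisons as 18; that it exceeds 5% held in every setting tried.

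The named secondary outcomes are not the source: FI and NEC alone give about 2–3% (exact) or 5–9% (uncorrected). For that reason the documents do not support a demand that NEC be tested only after FI. They do not rank one above the other, and such a gate would be post hoc if the data are already known. This is a worthwhile, cheap clarification and leaves the primary analysis untouched.

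**What to change.** Change sections 2.5(a), 2.5(b) and 1.5.2 together:

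1. State that FI and NEC, compared between groups, are the only secondary gut outcomes on which a conclusion may rest.
2. Label the nine individual findings exploratory in both the between-group and the in-place versus after-removal comparison.
3. Report each as counts and a difference with a 95% interval, and state that no conclusion about UVC and the gut rests on any one of them.
4. Section 1.1 dates the study from February 2023 to February 2024 and the methods are in the past tense. If results are already known, say that the label was set afterwards.

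The cost is a few sentences, with no new data and no more infants. The downside is that no significance claim can be made for a single gut finding.

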**1.2. Patient Enrollment and Group Formation**

The inclusion criteria were as follows: (1) parents agreed to participate in the study (2) infants born in our hospital, who were followed up in the NICU, with a gestational age of <34 weeks and a birth weight of 1000-2000 grams. Infants who indicated UVC placement, and for whom NIRS measurements were taken both before and after UVC placement were included in the UVC (+) Study Group. Infants who did not have a UVC but matched the Study Group regarding gestational age and birth weight constituted the UVC (-) Control Group.

Infants who died during the first week of life, were transferred to another hospital, had chromosomal anomalies, major congenital anomalies affecting splanchnic bed monitoring (such as congenital heart disease, abdominal wall defects, or congenital diaphragmatic hernia), inherited metabolic disorders, hydrops fetalis, TORCH infections, multiple organ failure, spontaneous intestinal perforation, lesions in the area where the NIRS sensor was placed, or

whose UVC was removed for any reason before 24 hours, as well as those with severe anemia or polycythemia, were excluded from the study. Infants with a birth hemoglobin (Hb) level of 10 g/dl or below were considered severely anemic, and those with a Hb level of 22 g/dl or above were considered polycythemic.

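### The within-UVC (+) comparison of gut findings, catheter in place versus after removal, sets no windows and takes no account of days at risk, so a much longer after-removal period can produce a false difference

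*Combined protocol and SAP*

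**What the plan says.** Section 2.5(a): "Clinical gastrointestinal and/or radiological findings observed during hospitalization were noted", followed by a list from vomiting and gastric residue to pneumatosis, portal venous gas and pneumoperitoneum. "These findings were evaluated both between the groups" and also "within the UVC (+) group, comparing the periods when the catheter was in place and after its removal". No length is given for either period.

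The catheter period is bounded elsewhere. Section 1.2 excludes infants "whose UVC was removed for any reason before 24 hours". Section 1.4 adds: "The recommended maximum duration of catheter use in our unit is 7-10 days for UVC". Nothing bounds the after-removal period before the end of the hospital stay. Section 2.5(b) sets 24-hour windows before and after removal, but for splanchnic oxygenation only.

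Section 1.5.2: "The McNemar-Bowker test was used for comparing categorical clinical findings at two different time points". No rate, person-time, offset or time-to-event method is listed. For confounding it says "Covariance analysis was used to assess the importance of the model that had been installed with the confounding factors", without tying this to the gut-findings comparison.

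The end of section 2.5(b) names rSO2S and FOE as primary outcomes, and feeding intolerance and NEC by UVC presence as secondary outcomes. The within-group gut-findings contrast is neither.

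**The concern.** If each infant is scored yes or no for a finding in each period, the longer period has more days in which to score yes. McNemar's test compares infants positive only in the first period with infants positive only in the second. It therefore registers a difference in period length as a difference in risk. A longer after-removal period makes the catheter look protective; a shorter one makes it look harmful.

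A second problem is separate from length. The catheter period always comes first, at a younger age and, on average, at lower feed volumes. Equalising the windows does not remove this.

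What is at stake is the reading of a supporting result. Gastric residue, vomiting and distension also define feeding intolerance, a secondary outcome, so a spurious within-group p-value on these signs could be taken as evidence about it.

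**Working it through.** **Inputs from the plan.** At least 21 infants per group (section 1.5.1); significance at p<0.05 (section 1.5.2); catheter in place from 24 hours to a recommended maximum of 7-10 days (sections 1.2 and 1.4). The plan gives no figure for this comparison. Its 21 per group for an effect size of 0.8 and 80% power reproduces with a one-sided t-test (20.03, rounded up); a two-sided t-test needs 26. Sidedness is not stated. Here 21 serves only as the number of pairs.

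**Assumed, because the documents give none.** Daily hazard of a finding, after-removal length, and how strongly risk is shared within an infant.

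**Formulas.** With daily hazard h and period lengths t1 (in place) and t2 (after), H1 = h·t1 and H2 = h·t2. The probability of no finding over cumulative hazard H is S(H) = exp(−H) if periods are independent, or (1+vH)^(−1/v) with gamma frailty of mean 1 and variance v.

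- Positive in place only: S(H2) − S(H1+H2)
- Positive after only: S(H1) − S(H1+H2)

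The rejection probability is an exact enumeration over 21 pairs, using the exact two-sided McNemar test.

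**One case in full.** h = 0.02, 7 v 28 days, independent, no catheter effect: H1 = 0.14, H2 = 0.56.

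- In place only: exp(−0.56) − exp(−0.70) = 0.571 − 0.497 = 0.075, or 1.6 of 21 infants.
- After only: exp(−0.14) − exp(−0.70) = 0.869 − 0.497 = 0.373, or 7.8 of 21.
- Discordant ratio 5.0; the test rejects in 43.1% of studies.

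**No catheter effect, % rejecting at h = 0.01 / 0.02 / 0.03 / 0.05**

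| Days in place v after | Independent | Frailty v=1 | Frailty v=2 |
|---|---|---|---|
| 7 v 7 | 0.1 / 0.8 / 1.5 / 2.1 | 0.1 / 0.5 / 0.9 / 1.5 | 0.1 / 0.3 / 0.6 / 0.9 |
| 7 v 10 | 0.3 / 1.9 / 3.4 / 5.2 | 0.2 / 1.2 / 2.2 / 3.5 | 0.15 / 0.8 / 1.4 / 2.2 |
| 7 v 14 | 1.4 / 6.4 / 10.8 / 17.4 | 0.9 / 4.2 / 7.2 / 11.1 | 0.6 / 2.8 / 4.7 / 7.0 |
| 10 v 28 | 10.9 / 27.6 / 39.1 / 52.5 | 7.4 / 18.8 / 25.8 / 31.9 | 5.0 / 12.5 / 16.8 / 20.1 |
| 7 v 28 | 16.3 / 43.1 / 59.7 / 76.6 | 11.3 / 30.9 / 43.0 / 54.3 | 7.8 / 21.5 / 29.9 / 37.5 |
| 1-10 v 7-35, uniform, per infant | 7.8 / 27.8 / 42.5 / 59.7 | 5.2 / 19.1 / 29.7 / 42.0 | 3.6 / 13.0 / 20.6 / 29.4 |

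If the last row is cut to the shorter of each infant's two periods, every cell is 1.6% or less.

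**Where it disappears or reverses.**

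- 7 v 28 days, hazard falling from 0.03 to 0.005 after day 14: 4.0%, 2.7%, 1.7% (v = 0, 1, 2). Falling from 0.05 to 0.02: 23.3%, 14.9%, 9.4%.
- Rare signs, h = 0.002, 7 v 28 days: 0.05% or less.
- After-removal period of 1 day against 7 in place: 3.3% at h = 0.02 and 36.4% at h = 0.05 (independent), now against the catheter.

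**What equal windows leave.** A hazard moving from 0.02 to 0.06 with age or feeding, over equal 7-day windows, rejects in 22.1%, 15.3%, 10.3% (v = 0, 1, 2). These are also the test's power for a true threefold difference. Over 4-day windows the figures are 9%, 6% and 4%.

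**Feed volume by section 1.3, uninterrupted.** Starting at 10 and rising by 10 ml/kg/day, the mean is 40 over days 1-7 and 110 over days 8-14. Starting at 40 and rising by 15, it is 85, then 149 (ceiling 150) or 171 (ceiling 180). The plan's full-feed mark of 120 needs (120−40)/15 = 5.3, so 6 whole increments, up to (120−10)/10 = 11. Some infants could reach it before a day 7-10 removal, so the gap in feed volume is an average one.

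**The case against.** The artefact needs two inferences. First, that the after-removal period runs to discharge: the text says when findings were noted, not where the comparison ends. Second, that McNemar-Bowker is applied to whole-period scores: section 1.5.2 speaks of time points, which fits status at defined moments at least as literally. The only windows around removal that the plan states are equal ones. They are stated for NIRS, but if the gut findings were bounded the same way, the length problem goes. The size also rests on assumed inputs: large values need about four weeks after removal at a roughly constant hazard, and the argument that age and feeding differ between periods weakens that constancy.

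Much of this stands. It limits the claim to a conditional one and keeps the severity down. It does not remove the point: the plan's wording contrasts periods, sets no window for them, and lists no method that uses days at risk.

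A reader might infer more: that the test is certain to be inflated, that the bias always favours the catheter, or that the study's main conclusions are affected. The documents support none of these. The method link is inferred, the direction depends on which period is longer, and neither primary nor secondary outcomes use this contrast. A reader might also infer that equal windows would make the contrast a fair test of the catheter. They would not, because the order is fixed.

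**Conclusion.** The point holds in conditional form, with low to moderate severity and medium confidence. On the natural reading, the comparison can show a difference that comes from period length alone. With 21 infants and assumed constant hazards of 0.01-0.05, that false signal is substantial when the after-removal period is about four times the catheter period. It is modest at twice the length, and negligible when the lengths are close, when the hazard falls steeply with age, or for rare signs. Actual stay lengths would settle which case applies; the documents do not give them. Whatever the lengths, age and feed volume remain confounded with period.

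**What to change.** 1. Do not run McNemar on whole, unequal periods. State where the after-removal period ends. By default, report each finding descriptively by period, with days at risk per infant and no p-value. Days at risk follow from the recorded placement and removal times and from hospitalization, read as length of stay (both in section 2.5).

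2. If a test is wanted for common signs and findings can be dated, there are two options. One is a within-infant days-at-risk comparison: a conditional binomial with expected share t1/(t1+t2). In simulations with no effect at 7 v 14 to 7 v 28 days and hazards 0.02-0.10, it rejected in 1.6-3.5%. It needs counts of episodes. The other is McNemar on the k days before and the k days after removal, with k the shorter of that infant's two periods. State that this discards later findings and has little power (about 22% or less for a threefold hazard difference over 7 days, about 9% or less over 4), so a null result is not evidence of no effect.

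3. State that age and feed volume are confounded with the fixed order, and do not read the contrast as a catheter effect. For that question use the between-group comparison, which also lacks a stated window: give the same follow-up window or days at risk for both groups. Note that it is observational, matched on gestational age and birth weight only, and that UVC (+) infants had an indication for the catheter.

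Cost: mainly analysis and reporting wording. The plan does not say that gut findings were dated, so option 2 may require retrieving dates from charts; the descriptive default needs only the period in which each finding occurred.

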## **1.5. Data analysis**

### **1.5.1. Sample size**

A power analysis was performed prior to the study using the summary values from our previous study, 'The Effect of Drip Versus Intermittent Feeding On Splanchnic Oxygenation In Preterm Infants With Intrauterine Growth Restriction: A Prospective Randomized Trial' (6). A sample size of at least 21 infants per group (UVC (+) versus UVC (-) group) was estimated to obtain statistically significant results with a Type-1 error rate of 0.05 (95% confidence level), an effect size of 0.8 (high), and 80% power.

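### The printed formula for FOE, a primary outcome, lacks brackets round the numerator; probably a notation slip, to be corrected and checked against the calculation code

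*Combined protocol and SAP*

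**What the plan says.** Section 2.5(b) of the combined protocol and SAP, on splanchnic NIRS monitoring, derives FOE from simultaneous SaO2 and rSO2S readings. It calls the derived values "the infants' fractional tissue oxygen extractions" and prints the formula as "FOE} = \text{SaO}_2 - \text{rSO}_2\text{S} / \text{SaO}_2". Without the typesetting codes this reads FOE = SaO2 − rSO2S / SaO2. The only parentheses are those of the sentence, which enclose the whole expression; none enclose the difference SaO2 − rSO2S. The sentence then interprets the values as ones "which represent the balance between oxygen delivery and oxygen consumption".

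Daily means of FOE over the first week of life are to be calculated after artifacts are removed. Later in the same section, FOE is named beside rSO2S in the statement that begins "The primary outcomes included comparing continuously recorded". It is compared between the UVC (+) and UVC (−) groups, and within the UVC (+) group around catheter placement and removal.

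The document gives no second definition of FOE, no worked value and no unit for it. The only saturation range it gives is for the pulse oximeter, "with a target band of 90–95% and alarm settings of 89 and 96% in the case of oxygen therapy".

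**The concern.** Division is done before subtraction, so the printed expression means SaO2 − (rSO2S / SaO2). A fractional extraction is the share of arterial oxygen that the tissue removes, (SaO2 − rSO2S) / SaO2. The formula and the name in the same sentence therefore describe different quantities.

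This is the sole specification of a derived primary variable, so someone who computes or replicates FOE from the text has only this line to work from. If it were coded literally on the fraction scale, the error would depend on SaO2. It would not cancel in a comparison between groups, between days, or before and after the catheter when SaO2 differs between the sides compared. The cohort is not randomised, so equal SaO2 in the two groups cannot be taken for granted.

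**Working it through.** **Figure to reproduce.** There is none: the document states no FOE value. Its one computed figure, the sample size in section 1.5.1, rests on a standardised effect size and does not use the FOE formula.

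**Inputs.** The formula and the SaO2 range of 90 to 95% (alarms 89 and 96%) come from section 2.5(b); that range applies to infants on oxygen therapy. The document gives no rSO2S values, so 0.40, 0.55 and 0.70 are assumed here for illustration.

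**Algebra.** Let S = SaO2 and r = rSO2S, both as fractions.

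- Bracketed: (S − r) / S = 1 − r/S
- Literal: S − r/S
- Literal minus bracketed: (S − r/S) − (1 − r/S) = S − 1

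The error does not involve r, so the assumed rSO2S values do not affect its absolute size. It is zero only at S = 1.00. It is linear in S, so the error in a daily mean is the mean SaO2 minus 1, and a difference in mean SaO2 between two groups is added in full to their FOE difference.

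**Fraction scale.**

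| SaO2 | rSO2S | Literal | Bracketed | Error |
|---|---|---|---|---|
| 0.90 | 0.40 | 0.456 | 0.556 | −0.10 |
| 0.90 | 0.55 | 0.289 | 0.389 | −0.10 |
| 0.90 | 0.70 | 0.122 | 0.222 | −0.10 |
| 0.95 | 0.40 | 0.529 | 0.579 | −0.05 |
| 0.95 | 0.55 | 0.371 | 0.421 | −0.05 |
| 0.95 | 0.70 | 0.213 | 0.263 | −0.05 |

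At the alarm limits the error is −0.11 (SaO2 0.89) and −0.04 (SaO2 0.96). The relative shortfall does depend on the assumed rSO2S. At SaO2 0.90 it runs from 0.10/0.556 = 18% to 0.10/0.222 = 45%; at 0.95, from 0.05/0.579 = 9% to 0.05/0.263 = 19%.

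**Two infants with the same true FOE of 0.30.** Here r = 0.70 × S.

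- S = 0.90, r = 0.630: literal = 0.90 − 0.70 = 0.20
- S = 0.95, r = 0.665: literal = 0.95 − 0.70 = 0.25

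The difference of 0.05 is the difference in SaO2 and nothing else.

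**Percent scale.** With SaO2 90 and rSO2S 70, the literal form gives 90 − 70/90 = 89.2. The bracketed form gives (90 − 70)/90 = 0.222, the same as on the fraction scale. With SaO2 95 and rSO2S 40, the literal form gives 95 − 40/95 = 94.6. In the target range the literal form thus returns about 89 to 95, which cannot be a fractional extraction.

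**The case against.** The strongest reply is that the intended formula is not in doubt. The name given in the same sentence fits only the bracketed form, so this is a typographical slip that no analyst would follow. That is probably right. It lowers the likely consequence but does not make the printed definition correct.

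A reader might go further and infer that the FOE results are biased, or that wrong values would pass unseen. The document supports neither. It contains no FOE value, code or output that points to the literal form. It quotes saturations in percent and describes no conversion to fractions, and in percent the literal form gives results near 90. An unseen error needs two undocumented steps: conversion to fractions, then literal coding.

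Three further points stand in part.

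- Brackets or a stacked numerator can be lost when a PDF is converted to text. This cannot be fully excluded, although the slash and the outer parentheses survived. The authors can settle it from their source file.
- The document describes a study already conducted, in the past tense, so the line may be a description and not the programming specification. A reader still has no other definition to use.
- The other primary variable, rSO2S, is measured directly and is unaffected.

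**Conclusion.** The definition is wrong as printed: it contradicts the name of the variable, concerns a primary outcome, and is corrected nowhere else in the document. If the literal form had been used on the fraction scale, FOE would be too low by 1 − SaO2, which is 0.05 to 0.10 across the stated oxygen-therapy target, and less for infants with higher saturation.

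That size is conditional. It assumes fractions and literal coding, and neither is shown. Distortion of the primary comparison would also need a difference in SaO2 between the groups or times compared, and the document reports no observed SaO2. The severity is therefore minor. It would become substantive only if a check of the calculation found the literal form in use.

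**What to change.** In section 2.5(b), print FOE = (SaO2 − rSO2S) / SaO2. State that SaO2 and rSO2S are entered in the same units and whether FOE is reported as a fraction or a percentage.

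Confirm from the calculation code or spreadsheet that the bracketed form was used, and recompute FOE and the analyses that depend on it only if it was not. A quick check is to recalculate a few readings by hand: values near 90, or values short of the bracketed result by 1 − SaO2, would show the literal form.

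The cost is one line of text and a check of one line of code. No new data are needed.
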